9.3 CORRELATION BETWEEN NEUTRALIZING ANTIBODY TITRES (MNA) AND IgG ANTIBODY TITRES (ELISA)

Correlation between neutralizing antibody titres (MNA) and IgG antibody titres (ELISA) will be presented as an exploratory analysis. For this, a scatter plot will be presented between neutralizing antibody titres and IgG antibody titres. Scatter plots will be grouped by the assessment visit days.

10 INTERIM ANALYSIS

An interim analysis will be performed once Part A of the study is completed i.e. when the last participant has completed Day 36 (14 days after the second vaccination). A second interim analysis will be performed after all participants have completed Day 106 visit. A third interim analysis will be performed after all participants have completed Visit 9.

11 SOFTWARE AND PROGRAMMING SPECIFICATIONS

All datasets, TLFs, and statistical analyses will be generated using SAS, Release 9.4 or higher (SAS Institute Inc., Cary, NC, USA). Computer-generated datasets, table, listing and figure output will adhere to the following specifications:

11.1 GENERAL PROGRAMMING SPECIFICATIONS

- One SAS program can create several outputs or a separate SAS program can be created for each output at statistical programmer's discretion.
- Each output will be stored in a separate file.
- Dataset files will be delivered in SAS7BDAT format.
- TLF output files will be delivered in Word format / rtf format (or the pdf format if sponsor requests).

11.2 TABLE, LISTING, AND FIGURE FORMAT

11.2.1 General

- All TLFs will be produced in landscape format, unless otherwise specified.
- All TLFs will be produced using the Courier New font, size 8.
- The data displays for all TLFs will have a 1.5-inch binding margin on top of a landscape- oriented page and a minimum 1-inch margin on the other 3 sides.
- Headers and footers for figures will be in Courier New font, size 8.
- Legends will be used for all figures with more than 1 variable, group, or item displayed.

- TLFs will be in black and white (no color), unless otherwise specified.
- Specialized text styles, such as bolding, italics, borders, shading, and superscripted and subscripted text, will not be used in the TLFs, unless otherwise specified. On some occasions, superscripts 1, 2, or 3 may be used (see below).
- Only standard keyboard characters will be used in the TLFs. Special characters, such as non-printable control characters, printer-specific, or font-specific characters, will not be used. Hexadecimal-derived characters will be used, where possible, if they are appropriate to help display math symbols (e.g., μ). Certain subscripts and superscripts (e.g., cm^2 , C_{max}) will be employed on a case-by-case basis.
- Mixed case will be used for all titles, footnotes, column headers, and programmer-supplied formats, as appropriate.

11.2.2 Headers

- All output should have the following header at the top left of each page:
 - For the Part A analysis:
Valneva Austria GmbH
Protocol: VLA2001-201
Part A Analysis
 - For the second interim analysis:
Valneva Austria GmbH
Protocol: VLA2001-201
Second Interim Analysis
 - For the third interim analysis:
Valneva Austria GmbH
Protocol: VLA2001-201
Third Interim Analysis
- All outputs should have Page n of N at the top or bottom right corner of each page. TLFs should be internally paginated in relation to the total length (i.e., the page number should appear sequentially as page n of N, where N is the total number of pages in the table).
- The date (date output was generated) should appear along with program name and location as the last footer on each page.

11.2.3 Display Titles

- Each TLF should be identified by the designation and a numeral. (i.e., Table 14.1.1). ICH E3 numbering is strongly recommended but sponsor preferences should be obtained prior to final

determination. A decimal system (x.y and x.y.z) should be used to identify TLFs with related contents. The title is centered. The analysis set should be identified on the line immediately following the title. The title and table designation are single spaced. A solid line spanning the margins will separate the display titles from the column headers. There will be 1 blank line between the last title and the solid line.

Table x.y.z
First Line of Title
Second Line of Title (if needed)
Analysis Set

11.2.4 Column Headers

- Column headings should be displayed immediately below the solid line described above in initial upper-case characters.
- Analysis set sizes will be presented for each treatment group in the column heading as (N=xx) (or in the row headings if applicable). This is distinct from the ‘n’ used for the descriptive statistics representing the number of participants in the analysis set.

11.2.5 Body of the Data Display

11.2.5.1 Table Conventions

- Units will be included where available
- Percentage values should be printed to one decimal place, in parentheses with no spaces, one space after the count (e.g., 7 (12.8%), 13 (5.4%)). Values that round down to 0.0 will be displayed as '<0.1'.
- The percentage of participants is normally calculated as a proportion of the number of participants assessed in the relevant treatment group (or overall) for the analysis set presented. However, careful consideration is required in many instances due to the complicated nature of selecting the denominator, usually the appropriate number of participants exposed. Details of this should be described in footnotes or programming notes.
- For categorical summaries (number and percentage of participants) where a participant can be included in more than one category, describe in a footnote or programming note if the participant should be included in the summary statistics for all relevant categories or just 1 category and the criteria for selecting the criteria.
- Where a category with a subheading (such as system organ class) has to be split over more than one page, output the subheading followed by “(cont)” at the top of each subsequent page. The overall summary statistics for the subheading should only be output on the first relevant page.

11.2.5.2 Listing Conventions

- Missing data should be represented on participant listings as either a hyphen (“-”) with a corresponding footnote (“- = unknown or not evaluated”), or as “N/A”, with the footnote “N/A = not applicable”, whichever is appropriate.
- Dates should be printed in SAS® YYMMDD10. format (“YYYY-MM-DD”: 2000-07-01). Missing portions of dates should be represented on participant listings as UNK (2000-07-UNK).
- All observed time values must be presented using a 24-hour clock HH:MM or HH:MM:SS format (e.g., 11:26:45, or 11:26). Time will only be reported if it was measured as part of the study.
- Units will be included where available

11.2.6 Footnotes

- A solid line spanning the margins will separate the body of the data display from the footnotes.
- All footnotes will be left-justified with single line spacing immediately below the solid line underneath the data display.
- Footnotes should begin with “Note:” if an informational footnote, or 1, 2, 3, etc. if a reference footnote. Each new footnote should start on a new line where possible.
- Footnotes will be present on the page where they are first referenced and thereafter on each page of the table, unless the footnote is specific only to certain pages. Participant specific footnotes should be avoided.
- Footnotes will be used as needed, however, it must add value to the table, listing, or figure. If more than six lines of footnotes are planned, then a cover page may be used to display footnotes, and only those essential to comprehension of the data will be repeated on each page.
- The last 2 lines of the footnote section will be a standard source that indicates the name of the program used to produce the data display, date the program was run, and the listing source (or data source for a listing) (i.e., ‘Program: myprogram.sas Listing source: 16.x.y.z’).

12 QUALITY CONTROL

12.1 SPECIFICATIONS

Once the SAP is finalized, dataset and TLF specifications will be developed and reviewed by the study team. An internal round table review of draft specifications will be conducted by the Lead Programmer, Lead Validator, Lead Statistician and Senior Reviewer (or member of Statistics Management).

The client will have the opportunity to review, comment and approve (via signature) all dataset and TLF specifications.

12.2 OUTPUTS

Validation of analysis datasets and tables are conducted through independent parallel programming of the statistical output according to the agreed upon specifications defined in the protocol, SAP, table shells, and dataset specifications. In this process, two programmers working independently (i.e., without input from one another), program the same output and compare results (via SAS PROC COMPARE). Any discrepancies are discussed and resolved, and the validation cycle is repeated until no further differences are noted between the two outputs.

All programs are submitted in batch mode to document the results of the PROC COMPARE indicating no unequal observations. Additionally, tracking logs are maintained which document all QC and validation findings and their resolution.

For CDISC datasets the Pinnacle 21 report will be used to validate the datasets for CDISC compliance.

Once the validation cycle is complete, the output (dataset or TLF) is subjected to the lead statisticians review as well as an internal round table review including the Lead Programmer, Lead Validator, Lead Statistician.

The client will have the opportunity to review, comment and approve (via signature) all final datasets and TLFs.

13 APPENDICES

13.1 CHANGES TO THE PROTOCOL SPECIFIED ANALYSES

As discussed with the sponsor, the analysis will not be stratified by serostatus for SARS-CoV-2 at screening because the chance that there are seropositive subjects enrolled in the study is negligible due to exclusion criteria #2 as per protocol.

13.2 INDEX OF TABLES

Table	Title	Population	Included in Interim Part A Analysis?	Included in Second Interim Analysis?	Included in Third Interim Analysis?
14.1.1	Participant Enrollment and Disposition Overall and by Sites	All Participants	Yes	Yes	Yes
14.1.2	Demographic and Baseline Characteristics	Safety	Yes	Yes	No
14.1.3	Medical and Vaccination History	Safety	No	No	No
14.1.4.1	Prior Medications	Safety	No	No	No
14.1.4.2	Concomitant Medications	Safety	No	No	No
14.1.5	Treatment Exposure	Safety	Yes	Yes	No
14.2.1.1	Overall Summary of Adverse Events	Safety	Yes	Yes	Yes
14.2.1.2	Solicited Injection Site Reactions Within 7 Days After Vaccination	Safety	Yes	Yes	No
14.2.1.3	Solicited Systemic Reactions Within 7 Days After Vaccination	Safety	Yes	Yes	No
14.2.1.4	Solicited Injection Site Reactions Within 7 Days After Vaccination By Maximum Severity	Safety	Yes	Yes	No
14.2.1.5	Solicited Systemic Reactions Within 7 Days After Vaccination By Maximum Severity	Safety	Yes	Yes	No
14.2.1.6	Overall Summary of Unsolicited Adverse Events	Safety	Yes	Yes	Yes
14.2.1.7	Summary of Unsolicited AEs Until Day 36	Safety	Yes	Yes	No
14.2.1.8	Summary of Unsolicited AEs Until Day 208	Safety	No	No	Yes
14.2.1.9	Summary of Serious Unsolicited AEs Until Day 36	Safety	Yes	Yes	No
14.2.1.10	Summary of Serious Unsolicited AEs Until Day 208	Safety	No	No	Yes

14.2.1.11	Summary of AESI Until Day 36	Safety	Yes	Yes	No
14.2.1.12	Summary of AESI Until Day 208	Safety	No	No	Yes
14.2.1.13	Summary of Treatment Related Unsolicited AEs Until Day 36	Safety	Yes	Yes	No
14.2.1.14	Summary of Treatment Related Unsolicited AEs Until Day 208	Safety	No	No	Yes
14.2.1.15	Summary of Unsolicited AEs by Maximum Severity Until Day 208	Safety	No	No	Yes
14.2.1.16	Summary of Unsolicited AEs by Causality Until Day 208	Safety	No	No	Yes
14.2.1.17	Summary of Follow-Up for participants at time of Data Cut for Day 106 analysis	Safety	No	Yes	No
14.2.1.18	Summary of Unsolicited AEs Until day of Data Cut for Day 106 analysis	Safety	No	Yes	No
14.2.1.19	Summary of Serious Unsolicited AEs Until day of Data Cut for Day 106 analysis	Safety	No	Yes	No
14.2.1.20	Summary of AESI Until day of Data Cut for Day 106 analysis	Safety	No	Yes	No
14.2.1.21	Summary of Treatment Related Unsolicited AEs Until day of Data Cut for Day 106 analysis	Safety	No	Yes	No
14.2.1.22	Summary of Unsolicited AEs by Maximum Severity until day of Data Cut for Day 106 analysis	Safety	No	Yes	No
14.2.1.23	Summary of Unsolicited AEs by Causality until day of Data Cut for Day 106 analysis	Safety	No	Yes	No
14.2.1.24	Solicited Injection Site Reactions Within 7 Days After Booster Vaccination	Safety (Booster)	No	No	Yes
14.2.1.25	Solicited Systemic Reactions Within 7 Days After Booster Vaccination	Safety (Booster)	No	No	Yes
14.2.1.26	Solicited Injection Site Reactions Within 7 Days After Booster Vaccination By Maximum Severity	Safety (Booster)	No	No	Yes
14.2.1.27	Solicited Systemic Reactions Within 7 Days After Booster Vaccination By Maximum Severity	Safety (Booster)	No	No	Yes

14.2.1.28	Duration of Solicited Injection Site Reactions after Booster Dose	Safety (Booster)	No	No	Yes
14.2.1.29	Duration of Solicited Systemic Reactions after Booster dose	Safety (Booster)	No	No	Yes
14.2.1.30	Overall Summary of Unsolicited Adverse Events (Booster Phase)	Safety (Booster)	No	No	Yes
14.2.1.31	Summary of Unsolicited AEs Up to Visit 9 (Booster Phase)	Safety (Booster)	No	No	Yes
14.2.1.32	Summary of Treatment Related Unsolicited AEs Up to Visit 9 (Booster Phase)	Safety (Booster)	No	No	Yes
14.2.1.33	Summary of Serious Unsolicited AEs Up to Visit 9 (Booster Phase)	Safety (Booster)	No	No	Yes
14.2.1.34	Summary of AESI Up to Visit 9 (Booster Phase)	Safety (Booster)	No	No	Yes
14.2.1.35	Summary of Unsolicited AEs Up to Visit 10 (Booster Phase)	Safety (Booster)	No	No	No
14.2.1.36	Summary of Treatment Related Unsolicited AEs Up to Visit 10 (Booster Phase)	Safety (Booster)	No	No	No
14.2.1.37	Summary of Serious Unsolicited AEs Up to Visit 10 (Booster Phase)	Safety (Booster)	No	No	No
14.2.1.38	Summary of AESI Up to Visit 10 (Booster Phase)	Safety (Booster)	No	No	No
14.2.1.39	Summary of Unsolicited AEs by Maximum Severity Up to Visit 9 (Booster Phase)	Safety (Booster)	No	No	Yes
14.2.1.40	Summary of Unsolicited AEs by Closest Causality Relationship Up to Visit 9 (Booster Phase)	Safety (Booster)	No	No	Yes
14.2.1.41	Summary of Unsolicited AEs by Maximum Severity Up to Visit 10 (Booster Phase)	Safety (Booster)	No	No	No
14.2.1.42	Summary of Unsolicited AEs by Closest Causality Relationship Up to Visit 10 (Booster Phase)	Safety (Booster)	No	No	No
14.2.2.1	Hematology: Summary and Change from Baseline	Safety	No	No	No
14.2.2.2	Hematology: Abnormal Clinically Significant Results	Safety	No	No	No
14.2.2.3	Biochemistry: Summary and Change from Baseline	Safety	No	No	No

14.2.2.4	Biochemistry: Abnormal Clinically Significant Results	Safety	No	No	No
14.2.2.5	Urinalysis: Summary and Change from Baseline	Safety	No	No	No
14.2.2.6	Urinalysis: Abnormal Clinically Significant Results	Safety	No	No	No
14.2.2.7	Urinalysis: Summary for Categorical Parameters	Safety	No	No	No
14.2.2.8	Coagulation: Summary and Change from Baseline	Safety	No	No	No
14.2.2.9	Coagulation: Abnormal Clinically Significant Results	Safety	No	No	No
14.2.2.10	Hematology: Summary and Change from Baseline (Booster Phase)	Safety (Booster)	No	No	No
14.2.2.11	Hematology: Abnormal Clinically Significant Results (Booster Phase)	Safety (Booster)	No	No	No
14.2.2.12	Biochemistry: Summary and Change from Baseline (Booster Phase)	Safety (Booster)	No	No	No
14.2.2.13	Biochemistry: Abnormal Clinically Significant Results (Booster Phase)	Safety (Booster)	No	No	No
14.2.2.14	Urinalysis: Summary and Change from Baseline (Booster Phase)	Safety (Booster)	No	No	No
14.2.2.15	Urinalysis: Abnormal Clinically Significant Results (Booster Phase)	Safety (Booster)	No	No	No
14.2.2.16	Urinalysis: Summary for Categorical Parameters (Booster Phase)	Safety (Booster)	No	No	No
14.2.2.17	Coagulation: Summary and Change from Baseline (Booster Phase)	Safety (Booster)	No	No	No
14.2.2.18	Coagulation: Abnormal Clinically Significant Results (Booster Phase)	Safety (Booster)	No	No	No
14.2.3	Vital Signs: Summary and Change from Baseline	Safety	No	No	No
14.2.3.1	Vital Signs: Summary and Change from Baseline (Booster Phase)	Safety (Booster)	No	No	No
14.2.4	Summary of Physical Examination Results	Safety	No	No	No

14.2.4.1	Summary of Physical Examination Results (Booster Phase)	Safety (Booster)	No	No	No
14.3.1.1	SARS-CoV-2 Neutralizing Antibodies (ND50) Over Timepoints	Per-Protocol	Yes	Yes	Yes
14.3.1.2	SARS-CoV-2 Neutralizing Antibodies (ND50) Over Timepoints	Modified Per-Protocol	Yes	Yes	Yes
14.3.1.3	SARS-CoV-2 Neutralizing Antibodies (ND50) Over Timepoints (Booster Participants)	Per-Protocol	No	No	Yes
14.3.1.4	SARS-CoV-2 Neutralizing Antibodies (ND50) Over Timepoints (Booster Participants)	Modified Per-Protocol	No	No	Yes
14.3.2.1	Proportion of Participants With Seroconversion in Terms of Neutralizing Antibodies (ND50): Secondary Immunogenicity Analysis	Per-Protocol	Yes	Yes	Yes
14.3.2.2	Proportion of Participants With Seroconversion in Terms of Neutralizing Antibodies (ND50): Secondary Immunogenicity Analysis	Modified Per-Protocol	Yes	Yes	Yes
14.3.2.3	Proportion of Participants With Seroconversion in Terms of Neutralizing Antibodies (ND50) (Booster Participants)	Per-Protocol	No	No	Yes
14.3.2.4	Proportion of Participants With Seroconversion in Terms of Neutralizing Antibodies (ND50) (Booster Participants)	Modified Per-Protocol	No	No	Yes
14.3.3.1	Fold Increase of SARS-CoV-2 Neutralizing Antibody Titres (ND50): Secondary Immunogenicity Analysis	Per-Protocol	Yes	Yes	Yes
14.3.3.2	Fold Increase of SARS-CoV-2 Neutralizing Antibody Titres (ND50): Secondary Immunogenicity Analysis	Modified Per-Protocol	Yes	Yes	Yes
14.3.3.3	Fold Increase of SARS-CoV-2 Neutralizing Antibody Titres (ND50) (Booster Participants)	Per-Protocol	No	No	Yes
14.3.3.4	Fold Increase of SARS-CoV-2 Neutralizing Antibody Titres (ND50) (Booster Participants)	Modified Per-Protocol	No	No	Yes

14.3.4.1	IgG antibody Titres Against SARS-CoV-2 S-protein, Determined by ELISA: Secondary Immunogenicity Analysis	Per-Protocol	Yes	Yes	Yes
14.3.4.2	IgG antibody Titres Against SARS-CoV-2 S-protein, Determined by ELISA: Secondary Immunogenicity Analysis	Modified Per-Protocol	Yes	Yes	Yes
14.3.4.3	IgG antibody Titres Against SARS-CoV-2 S-protein, Determined by ELISA (Booster Participants)	Per-Protocol	No	No	Yes
14.3.4.4	IgG antibody Titres Against SARS-CoV-2 S-protein, Determined by ELISA (Booster Participants)	Modified Per-Protocol	No	No	Yes
14.3.5.1	Proportion of Participants With Seroconversion in Terms of S-protein specific IgG Antibodies: Secondary Immunogenicity Analysis	Per-Protocol	Yes	Yes	Yes
14.3.5.2	Proportion of Participants With Seroconversion in Terms of S-protein specific IgG Antibodies: Secondary Immunogenicity Analysis	Modified Per-Protocol Day 208	Yes	Yes	Yes
14.3.5.3	Proportion of Participants With Seroconversion in Terms of S-protein specific IgG Antibodies (Booster Participants)	Per-Protocol	No	No	Yes
14.3.5.4	Proportion of Participants With Seroconversion in Terms of S-protein specific IgG Antibodies (Booster Participants)	Modified Per-Protocol	No	No	Yes
14.3.6.1	Fold Increase of SARS-CoV-2 S-protein specific IgG Antibody Titres Determined by ELISA: Secondary Immunogenicity Analysis	Per-Protocol	yes	Yes	Yes
14.3.6.2	Fold Increase of SARS-CoV-2 S-protein specific IgG Antibody Titres Determined by ELISA: Secondary Immunogenicity Analysis	Modified Per-Protocol	yes	Yes	Yes
14.3.6.3	Fold Increase of SARS-CoV-2 S-protein specific IgG Antibody	Per-Protocol	No	No	Yes

	Titres Determined by ELISA (Booster Participants)				
14.3.6.4	Fold Increase of SARS-CoV-2 S-protein specific IgG Antibody Titres Determined by ELISA (Booster Participants)	Modified Per-Protocol	No	No	Yes
14.4.1.1	Cellular Immune Response (T-Cell Response) measured by IFNgamma ELISpot: Exploratory Analysis	Per-Protocol	Yes	Yes	Yes
14.4.1.2	Cellular Immune Response (T-Cell Response) measured by IFNgamma ELISpot: Exploratory Analysis	Modified Per-Protocol	Yes	Yes	Yes
14.4.1.1.1	Cellular Immune Response (T-Cell Response) measured by IFNgamma ELISpot (Booster Participants)	Per-Protocol	No	No	Yes
14.4.1.2.1	Cellular Immune Response (T-Cell Response) measured by IFNgamma ELISpot (Booster Participants)	Modified Per-Protocol	No	No	Yes
14.4.1.3	Cellular Immune Response measured by IFNgamma ELISpot (Reactogenicity against stimulation panel): Exploratory Analysis	Per-Protocol	Yes	Yes	Yes
14.4.1.4	Cellular Immune Response measured by IFNgamma ELISpot (Reactogenicity against stimulation panel): Exploratory Analysis	Modified Per-Protocol	Yes	Yes	Yes
14.5.1.1	SARS-CoV-2 Neutralizing Antibody Titres (ND50) Over Timepoints	Per-Protocol (Plus Convalescent Participants)	Yes	Yes	Yes
14.5.1.2	SARS-CoV-2 Neutralizing Antibody Titres (ND50) Over Timepoints	Modified Per-Protocol (Plus Convalescent Participants)	Yes	Yes	Yes
14.6.1.1	Cellular Immune Response Measured by ICS: %CD4+ T-Cells for Each Singular Cytokine and Stimulation Panel	Per-Protocol	No	Yes	Yes
14.6.1.2	Cellular Immune Response Measured by ICS:%CD4+ T-Cells for Each Singular Cytokine and Stimulation Panel	Modified Per-Protocol	No	Yes	Yes

14.6.1.3	Cellular Immune Response Measured by ICS:%CD8+ T-Cells for Each Singular Cytokine and Stimulation Panel	Per-Protocol	No	Yes	Yes
14.6.1.4	Cellular Immune Response Measured by ICS: %CD8+ T-Cells for Each Singular Cytokine and Stimulation Panel	Modified Per-Protocol	No	Yes	Yes
14.7.1.1	SARS-CoV-2 Neutralizing Antibodies (ND50) Over Timepoints (Booster Phase)	ITT (Booster)	No	No	Yes
14.7.2.1	Fold Increase of SARS-CoV-2 Neutralizing Antibody Titres (ND50) (Booster Phase)	ITT (Booster)	No	No	Yes
14.7.3.1	Proportion of Participants With 4-Fold Increase in Terms of Neutralizing Antibodies (ND50) (Booster Phase)	ITT (Booster)	No	No	Yes
14.7.4.1	IgG antibody Titres Against SARS-CoV-2 S-protein, Determined by ELISA (Booster Phase)	ITT (Booster)	No	No	Yes
14.7.5.1	Fold Increase of SARS-CoV-2 S-protein specific IgG Antibody Titres Determined by ELISA (Booster Phase)	ITT (Booster)	No	No	Yes
14.7.6.1	Proportion of Participants With 4-Fold Increase in Terms of in Terms of S-protein specific IgG Antibodies (Booster Phase)	ITT (Booster)	No	No	Yes
14.8.1.1	Cellular Immune Response (T-Cell Response) measured by IFNgamma ELISpot (Booster Phase)	ITT (Booster)	No	No	Yes
14.9.1.1	Cellular Immune Response Measured by ICS: %CD4+ T-Cells for Each Singular Cytokine and Stimulation Panel (Booster Phase)	ITT (Booster)	No	No	Yes
14.9.1.2	Cellular Immune Response Measured by ICS:%CD8+ T-Cells for Each Singular Cytokine and Stimulation Panel (Booster Phase)	ITT (Booster)	No	No	Yes

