## **8.5 Rationale and Justification for the Booster Phase.**

Following the successful completion of the Part A primary analysis (Day 36), the high dose was found to be the optimal dose as defined in the primary objective of the study. Based on the assessed comparable safety and superior immunogenicity results at Day 36, the high dose has been selected for further clinical development. Valneva has decided to extend the VAL2001-201 study, by investigating the effects of a Booster dose at 8-9 months after completion of the primary immunization schedule with VLA2001. The booster dose will be offered to all participants who do not meet an exclusion criteria regardless of their initial response to the primary immunization schedule in the different dose groups. Hence, the effect of a booster dose will be studied in a population with different levels of pre-existing antibody levels against SARS-CoV-2.

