### **16.4.3 Secondary Endpoints**

#### **16.4.3.1 Secondary Safety Endpoints**

The number and percentage of Participants with unsolicited AEs (including those with clinically relevant laboratory parameter changes), related AEs, AESIs and SAEs will be presented for each study arm, overall, by system organ class/preferred term and by severity. Differences between study groups will be assessed for significance using Fisher's exact (Fisher-Freeman-Halton) test, whereby a significant overall test will be amended by pair-wise tests, and 95% confidence interval (CI) will be presented for all AE rates.

The number and percentage of Participants with abnormal laboratory parameters will be presented for each study arm, overall and by parameter.

Further details will be provided in the Statistical Analysis Plan (SAP).

All analyses of safety data will be based on the SAS.

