3.1.2 Secondary Endpoints

- Frequency and severity of any unsolicited AE until Day 36.
- Frequency and severity of any vaccine-related AE until Day 36.
- Frequency and severity of any AE until Day 208.
- Frequency and severity of any vaccine-related AE until Day 208.
- Frequency and severity of any SAE until Day 36.
- Frequency and severity of any AESI until Day 36.
- Frequency and severity of any SAE until Day 208.
- Frequency and severity of an AESI until Day 208.

Booster Phase:

- Frequency and severity of solicited AEs (local and systemic reactions) within 7 days after the booster vaccination
- Frequency and severity of any unsolicited AE up to Visit 9
- Frequency and severity of any vaccine-related AE up to Visit 9
- Frequency and severity of any SAE up to Visit 10
- Frequency and severity of any AESI up to Visit 10

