In addition, following summaries will be presented by SOC and PT for each dose cohort and overall:

- Summary of unsolicited AEs until Day 36
- Summary of unsolicited AEs until Day 208
- Summary of serious unsolicited AEs until Day 36
- Summary of serious unsolicited AEs until Day 208
- Summary of AESI until Day 36
- Summary of AESI until Day 208
- Summary of treatment related unsolicited AEs until Day 36
- Summary of treatment related unsolicited AEs until Day 208

- Summary of unsolicited AEs by maximum severity
- Summary of unsolicited AEs by closest causality relationship

The following summaries of adverse events presented by SOC and PT will be added for the additional interim analysis after Day 106:

- Participants with any unsolicited AE until day of Data Cut for Day 106 analysis
- Participant with any serious unsolicited AE until day of Data Cut for Day 106 analysis
- Participant with any AESI until day of Data Cut for Day 106 analysis
- Participants with any treatment related unsolicited AE until day of Data Cut for Day 106 analysis
- Summary of unsolicited AEs by maximum severity until day of Data Cut for Day 106 analysis
- Summary of unsolicited AEs by closest causality relationship until day of Data Cut for Day 106 analysis

Participants with multiple adverse events within an SOC or SOC/PT combination are counted only once for that SOC or SOC/PT combination. For the summary table of AEs by maximum severity, if a participant experiences multiple events in the same SOC or SOC/PT combination, the highest recorded severity will contribute counts to the summary table. For the summary table of AEs by closest causality relationship, if a participant experiences multiple events in the same SOC or SOC/PT combination, the closest relationship to study drug will contribute counts to the summary table. All data from the adverse events eCRF will also be listed.

Booster Phase:

An overall summary of adverse events will be presented separately for the booster phase and will include:

- Participants with any unsolicited AE up to Visit 9 in the booster phase
- Participants with any treatment related unsolicited AE up to Visit 9 in the booster phase
- Participant with any serious unsolicited AE up to Visit 9 in the booster phase
- Participant with any AESI up to Visit 9 in the booster phase
- Participants with any unsolicited AE up to Visit 10 in the booster phase
- Participants with any treatment related unsolicited AE up to Visit 10 in the booster phase

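### The SAP plans no by-dose severity table for unsolicited AEs until Day 36, and no separate severity table for related unsolicited AEs, SAEs or AESIs at any time, although the endpoints and Protocol 16.4.3.1 call for severity

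*SAP*

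**What the plan says.** **Endpoints.** SAP 3.1.2 lists eight secondary safety endpoints for the primary phase and five for the booster phase. All thirteen cover frequency and severity. An example for the Day 36 window is "Frequency and severity of any vaccine-related AE until Day 36". Three more in the same form cover unsolicited events, SAEs and AESIs to that day.

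**Protocol analysis.** Protocol 16.4.3.1 names four classes of event (unsolicited, related, AESI and SAE) and says of their numbers and percentages that they "will be presented for each study arm, overall, by system organ class/preferred term and by severity".

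**SAP analysis.** For the primary phase, SAP 7.2.1 names "Summary of unsolicited AEs by maximum severity" with no cut-off day, plus a version for the Day 106 data cut. For the booster phase it names versions to Visit 9 and Visit 10. The rows listed for the overall summary are any, serious, AESI, treatment-related and medically attended events. No row concerns severity.

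**SAP index.** SAP 13.2 turns the undated line into "Summary of Unsolicited AEs by Maximum Severity Until Day 208" (Table 14.2.1.15), marked No for Part A, No for the second interim and Yes for the third.

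**Declared changes.** SAP 13.1 declares one change from the protocol analyses, the dropped stratification by screening serostatus.

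**The concern.** An endpoint defined by frequency and severity is only half reported by a count of participants with an event. In such a count, a mild related event and a Grade 3 related event weigh the same. If severity rose with dose while frequency stayed similar, the count tables for unsolicited events until Day 36 would not show it.

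Day 36 is also the window that mattered for dose. Protocol 8.5 states: "Based on the assessed comparable safety and superior immunogenicity results at Day 36, the high dose has been selected for further clinical development". Protocol 10.6.2 has a suspension criterion that counts participants in one dose group with the same Grade 3 unsolicited AE within 36 days of first vaccination. The protocol therefore treats the grade of unsolicited events, by dose group and in this window, as information worth acting on. No indexed table displays it.

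**Working it through.** The point rests on no sample-size or alpha figure, so there is no plan figure to reproduce. The check is a count of the tables in SAP 13.2 that carry maximum severity in the title, set against the endpoints.

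| Table | Content | Part A | 2nd interim | 3rd interim |
|---|---|---|---|---|
| 14.2.1.4 | Solicited injection-site, primary series | Yes | Yes | No |
| 14.2.1.5 | Solicited systemic, primary series | Yes | Yes | No |
| 14.2.1.15 | Unsolicited, to Day 208 | No | No | Yes |
| 14.2.1.22 | Unsolicited, to Day 106 data cut | No | Yes | No |
| 14.2.1.26 | Solicited injection-site, booster | No | No | Yes |
| 14.2.1.27 | Solicited systemic, booster | No | No | Yes |
| 14.2.1.39 | Unsolicited, booster to Visit 9 | No | No | Yes |
| 14.2.1.41 | Unsolicited, booster to Visit 10 | No | No | No |

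**Counts.**
- There are 8 severity tables: 4 solicited and 4 unsolicited.
- Part A has 2 of the 8, both solicited, so 0 of the 4 unsolicited tables.
- The second interim has 3, of which 1 is unsolicited. The third interim has 4, of which 2 are unsolicited.
- Tables that show related AEs, SAEs or AESIs as a separate class by severity: 0 of 8.

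**Day 36 compared with the other cuts.** Day 36 has unsolicited-event tables for all events, serious events, AESIs and related events (14.2.1.7, .9, .11, .13). No severity table accompanies them. The Day 106 cut, Day 208, Visit 9 and Visit 10 each have one severity table for all unsolicited events. Table 14.2.1.15 includes events before Day 36 but cannot isolate them, because it accumulates to Day 208.

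**Are the data there?** Yes. Protocol 15.2.1 records severity for each AE, and SAP 7.2.1 already sets the rule that the most severe grade counts.

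**What could such a table detect?** The documents give no Grade 3 rates, so those below are assumptions. With n = 50 per group and a two-sided Fisher's exact test at 0.05, power is the sum over all (a, b) with Fisher p ≤ 0.05 of Bin(a; 50, p1) × Bin(b; 50, p2).

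| Assumed Grade 3 rates | Power |
|---|---|
| 2% vs 10% | about 19% |
| 2% vs 15% | about 51% |
| 2% vs 20% | about 78% |

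The table would mainly describe. It would not support a firm claim of similarity or difference.

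**The case against.** The strongest reply is that a missing index row says little about what was known when the dose was chosen. A reader might infer that the choice had no severity comparison behind it, and the documents do not support that:

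- Solicited reactions are tabulated by severity in Part A (14.2.1.4 and 14.2.1.5).
- The participant-level listing of unsolicited AEs (16.2.1.2) is marked for Part A, and SAP 7.2.1 says all data from the AE form are listed.
- Protocol 15.11.3 has the DSMB reviewing unblinded listings and tabulations of unsolicited AEs and SAEs.
- Grade 4 events are reported as SAEs (Protocol 15.1.2), so they should appear in the Part A table of serious events.
- Protocol 8.5.1 describes Day 36 AEs as mostly mild or moderate, though without separating solicited from unsolicited.

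This SAP also postdates Part A. It is based on a protocol version dated 31 August 2021, Protocol section 5 puts the end of Part A in February 2021, and SAP section 8 speaks of the Day 36 analysis as already performed. Its Part A column is not a clean record either: Figures 1.6.5 and 1.6.6, for Day 106 and Day 208, are marked Yes for Part A. Table shells are separate specifications (SAP section 12) and are not in the documents, so the content of Table 14.2.1.1 is known only by its title.

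A reader might also count nearly every secondary endpoint as having no severity table at all. That overstates it. Protocol 15.2.1.2 treats solicited injection-site reactions as related, and these are graded in 14.2.1.4 and 14.2.1.26, so the related-AE endpoints are partly covered. Unsolicited SAEs and AESIs until Day 208 fall within 14.2.1.15, though they cannot be picked out.

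These replies limit what can be said about the dose choice. They do not answer the reporting gap. A listing is not a summary by arm and by severity, and SAP 13.1 does not say that the protocol commitment was dropped.

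**Conclusion.** The point holds as a gap between stated endpoints and planned output. SAP 7.2.1 and 13.2 index no by-dose severity table of unsolicited AEs until Day 36. They index no separate severity table for related unsolicited AEs, SAEs or AESIs at any time, and SAP 13.1 does not declare the omission. This goes beyond missing detail, because following the SAP as written leaves the Protocol 16.4.3.1 commitment unmet.

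In size, 0 of 4 unsolicited severity tables serve Day 36, and 0 of 8 severity tables show the three narrower classes separately. For the dose choice, the documents support only this: no tabulated by-dose severity comparison of unsolicited AEs is indexed for Part A.

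The conclusion assumes that the table titles and the rows listed in SAP 7.2.1 reflect what the unseen shells contain.

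**What to change.** In SAP 7.2.1 and 13.2:

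1. Add unsolicited AEs by maximum severity until Day 36, by dose group and overall.
2. Add treatment-related unsolicited AEs by maximum severity until Day 36, until Day 208, and to booster Visit 9.
3. Add severity rows, or a Grade 3-or-higher row, to the overall summaries for unsolicited AEs, related AEs, SAEs and AESIs.
4. Mark these for the third interim and final reports, since the Part A analysis is already done, and label them descriptive.

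If the sponsor prefers not to add them, SAP 13.1 should declare and justify the omission.

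The cost is SAP wording and a few extra tables from data already collected. The small downside is that many cells will be sparse, especially for SAEs and AESIs, which is why rows in the overall summary are enough for those two classes.
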